## B. Methods to develop study groups

Because this is a descriptive evaluation, this subsection is not relevant.

## C. Sample

Recruitment into the FRAMEWorks Program and the study rely heavily on referrals from past participants and community partners who serve eligible participants in their respective target populations. Referrals will come from the AVANCE-Houston website that presents available programs and services, advertising by AVANCE-Houston staff about the program, and word of mouth from current and past participants. Recruitment targets largely low-income parents or individuals in the Houston area who are: at least 18 years of age with no open criminal cases

**Commented [DF1]:** It might be good to note your sample size here. I know it is in your diagram, but it could be noted here as well.

(can be deferred); have children up to 24 years; and are interested in services (see Table 6 below).

**Table 6: Target population for analytic sample**

Description of Target Population	How is the population different from those who will be broadly served by the grant?	How will the target population be identified?	Unit of Analysis
Adults who are primarily low-income and 18+ years of age	No difference, all program participants will be offered a chance to enroll in the evaluation study. Those who do not are still eligible for the program.	AVANCE and community partners will recruit potential participants through informational flyers and targeted recruitment at community events (e.g., open houses, career fairs, Head Start centers, etc.). AVANCE program staff will determine eligibility for program participation.	Individual

Staff present the purpose and benefits of program services at orientations held at partner sites to recruit eligible parents. Orientations also discuss the descriptive study and explain informed consent before soliciting study participation. Participant responsibilities are clarified at the orientation, such as providing contact information and responding to surveys.

**Table 7: Methods to Promote Sufficient Program Participation**

What methods will you use to ensure sufficient sample is recruited, enrolls, and participates in the program?	AVANCE and their community partners will recruit program participants, and AVANCE will provide incentives for program retention and completion. The CQI process will address issues regarding program recruitment and enrollment to ensure targets are met.
Who will be responsible for recruiting the evaluation sample?	The evaluation sample may differ from the program population, in that all participants will be invited to participate in the evaluation. Any participant who declines to enroll in the evaluation will still be eligible for the program. Enrollment into the evaluation will be conducted by the CQI Data Manager who will conduct the informed consent process and proctor the baseline data collection efforts.
Please describe any incentives to be offered for program	Program Participation – AVANCE will provide a series of incentives for program retention (promotional items) and completion (\$100 gift card).

*participation and/or completion and/or data collection and/or participation in the evaluation.*

Evaluation Participation – No incentives will be used for baseline data collection. A \$50 incentive will be used for the 1-year follow-up survey and will be provided in the form of a Walmart or PayPal gift card.

#### D. Lead staff

Evaluators for this study comprise an experienced group with many years of experience investigating HMRF Projects. Each staff member has a specific role in the evaluation project as summarized below in Table 8 and subsequent discussion (see CVs in Appendix B for more details on the qualifications of evaluation staff for this project).

## E. Ongoing coordination between grantee and local evaluator

The basis for ongoing coordination between AVANCE (the grantee) and MER (the local evaluator) is regular communication, by way of recurring meetings and daily interactions with embedded staff. Throughout the original proposal process, and now during the evaluation planning phase, MER worked in consort with AVANCE to design a study with research questions that are appropriate to the intervention. MER guides the process, given our experience designing and running evaluations, and AVANCE provides expertise on their community, target population, and program/curricula specifics.

Recurring meetings will include a bi-weekly project CQI team meeting. Under the leadership of the Data Manager and Lead MER Evaluator, the CQI team reviews data from the nFORM and local evaluation systems to identify and mitigate implementation or data issues, and closely examine trends and accomplishments. This team includes AVANCE organizational and project leadership, the MER Evaluation team, and front-line staff representatives (e.g., Program Administrators, Case Managers).

In addition to CQI team meetings, overall project team meetings occur monthly (at a minimum), with project leaders across MER and AVANCE in attendance, to ensure the partnership remains strong and that coordination across organizations is on track. This recurring, ongoing meeting structure is conducive to close coordination, ensuring that challenges can be quickly addressed, and promising strategies can be efficiently maximized.

One of the key components of this coordination effort is the CQI Data Manager, who is a MER employee, embedded with AVANCE. The CQI Data Manager functions to bridge the gap between organizations. They will interact with AVANCE staff daily while completing their job duties and play a leadership role in the recurring meetings outlined above. See Section II.D above for more details about this role and others. Both the meetings and the roles outlined above will continue throughout the entire project period, providing opportunities to ensure the rigor and relevance of the evaluation and its findings, and to discuss and coordinate dissemination efforts (which will also be shared across MER and AVANCE).

MER has experience operating prior descriptive evaluations using this exact process. Clearly outlining roles and responsibilities maintains the independence of the evaluation. That is, the evaluation team helps identify and illuminate areas of concern or improvement (for the program and the evaluation), but the program staff have responsibility for implementing improvements and providing direct services to participants. In this way, AVANCE and MER acknowledge our shared interest in and responsibility for a well-executed project and evaluation, but that MER is also an independent and external organization with a high level of integrity and is not responsible for nor invested in the specific outcomes of the program. This allows for close coordination without allowing for co-dependence, or for personal interests to influence evaluation findings.

### III. Data Collection

#### A. Constructs and Measures

Table 9 below summarizes the constructs of interest, measures to evaluate those constructs, and specific data collection instruments.

**Table 9: Constructs and measures/data collection instruments**

Construct	Measure and description	Instrument	Reliability and Validity (if standardized instrument, you provide a citation for the instrument)
Parenting Attitudes	4 items: levels of agreement for parent relationship status best for child (categories, 4-point scale)	OLLE (Q1-4)	Psychometric analyses of parenting attitudes construct completed in October 2021 (a = .862)
Partner Relationship Attitudes	5 items: levels of agreement with attitudes about relationship (categories on 5-point scale)	Healthy Marriage Adult Program Survey (D10.a-e)	nFORM
Parenting Behaviors	4 items: frequency supporting child (categories on 4-point scale)	Healthy Marriage Adult Program Survey (A2a.a-d)	nFORM
Partner Relationship Behaviors	3 items: frequency engaged in key behaviors with partner (categories, 4-point scale)	Healthy Marriage Adult Program Survey (D11.a-c)	nFORM
Financial Readiness Behaviors	2 items: have checking/savings account (yes/no)	Healthy Marriage Adult Program Survey (B3a-b)	nFORM
Job Readiness Behaviors	1 item: do you have an update resume you can give to employers (yes/no)	Healthy Marriage Adult Program Survey (B2)	nFORM

#### B. Consent

Because the planned evaluation involves human subjects, AVANCE understands program implementation requires both IRB approval and participant informed consent. MER has an established relationship with Solutions IRB, having secured more than 20 IRB approvals and renewals for evaluations it has conducted during the past five years. IRB clearance will be submitted for approval and obtained during the planning period.

To secure informed consent, participants will attend an orientation/enrollment session where the Data Manager will describe the evaluation process and the risks and benefits of the project. At this point in time, participants have not yet taken entrance surveys (including the ACS) and are therefore not yet enrolled in the program or the study. Enrollment immediately follows consent. Those participants that wish to participate in the evaluation will complete an informed consent process and affirm their consent on the OLLE Entrance Survey in the form of a survey question. All participants will receive a copy of the consent form with contact information for evaluation staff and how to contact the IRB if needed. Informed consent will take place prior to study enrollment and the collection of evaluation data. Those participants who initially indicate they do not wish to participate in the evaluation study will be referred to a family coach who will work with that person to explain study benefits. If they still refuse to enroll in the evaluation study, they are still eligible to participate in the program and receive services.

### C. Data Collection

Implementation study data from nFORM will be collected bi-weekly and reviewed with regard to enrollment, retention, participation, survey completion, etc. This data is updated in real time by the evaluator and reviewed with grantee staff during scheduled bi-weekly CQI meetings. These meetings are designed to keep the evaluator informed about project updates, progress toward program targets, and to discuss any interventions that might need to be developed.

In addition to the bi-weekly CQI meetings between the evaluator and the grantee staff, MER will conduct a yearly site visit either in person or virtually. Evaluation staff will meet with program leadership, support staff (facilitators, family coaches, career coaches, etc.), and participants (past and present if possible) in an interview style setting. Questions will aim to seek information about how the program is progressing, what we have learned so far, if there are issues the evaluation staff can identify that might need to be addressed, and to provide guidance on how to run the program better. MER will create a report of the information discussed in the site visit that will be shared with program staff and the program ETAP.

Survey administration procedures collect data for outcomes assessment that are carried out by case managers under supervision of the CQI Data Manager. Evaluation data collection occurs at two time points – nFORM and OLLE entrance surveys at wave 1 before primary workshops begin and the 1-year follow-up OLLE survey at wave 2 one year after program enrollment. Table 10 below presents the timing of collection for each wave.

**Table 10: Timeline**

Wave of Data Collection (e.g., baseline, short-term follow-up, long-term follow-up)	Timing of Data Collection
Entrance (nFORM and OLLE)	Collected immediately after informed consent and enrollment – during orientation or first workshop.

One-year follow-up (1 year post-enrollment, OLLE only)

Collected approximately one year after project enrollment. MER's survey tracking team will reach out 60-days prior to the one year mark and will stop attempting to collect follow-up surveys 30 days after the due date.

**Table 11: Measures**

Measure	Timing of Data Collection (baseline, wave of data collection)	Method of Data Collection	Who Is Responsible for Data Collection?	Will Methods or Collection Procedures Differ by Study Group?	Administrative Data Only: Will data access require data sharing agreement?
nFORM Applicant Characteristics (ACS) Survey	At enrollment	Participant self-enters survey using online data collection platform (nFORM)	AVANCE staff will proctor data collection and assist participants as necessary	No	N/A
On-line Local Evaluation (OLLE) and nFORM Entrance Survey	At enrollment	Participant self-enters survey using online data collection platforms (Qualtrics and nFORM, respectively)	AVANCE staff will proctor data collection and assist participants as necessary	No	N/A
OLLE One-Year Follow-up Survey	1 year after enrollment / baseline	Participant self-enters survey using online data collection platform and link – or – Phone interview data collection	MER Research Staff/ participant tracking team	No	N/A

### Ensuring and monitoring high quality data collection

This evaluation will utilize the nFORM and OLLE entrance surveys at enrollment and the OLLE 1-year follow-up surveys collected one year after enrollment. The data collection methods for these time points differ, as shown in Table 11 above and as discussed further in Table 12 below.

All program staff and evaluation staff will undergo a rigorous set of trainings to prepare for the evaluation. All staff receive an overview and introductory training to present the goals and objectives of the evaluation effort and its importance to the overall project. Next, all staff receive training on human subject protection and are required to pass a certification test on the subject matter. All staff will also receive a detailed training on the evaluation, including the

evaluation tools, timing and data collection process, and the role and importance of randomization of participants.

In addition, the data manager and the primary local evaluation staff will undergo a rigorous training process to better understand the context of HMRP research, training on data collection procedures they will be responsible for, and training on the nFORM system and use of nFORM data in a CQI process. MER is creating networks of CQI data managers and Evaluation Project Managers across the 12 projects that we are evaluating so that all staff have access to experienced data managers and evaluation staff who have done this work previously. This training takes the form of weekly training sessions that are currently underway.

Members of the CQI team will also receive specific training on the MER CQI process that has been developed prior to the launch of data collection or program services. As described elsewhere, MER is assisting the program staff in implementing a robust CQI process that will focus on retention as one of the primary areas of program improvement, and as such, we are anticipating relatively modest levels of attrition for this data collection.

On a bi-weekly basis, the data manager, the local evaluation staff, and MER technical specialists will be responsible for downloading data from the nFORM and MER On-Line Local Evaluation (OLLE) systems for processing and presentation to the CQI team for tracking and monitoring performance measurement outcomes (recruitment, enrollment, dosage, completion, referrals, etc.) so that near real-time adjustments can be made to program implementation to ensure compliance with program goals and objectives.

All MER training is currently being recorded, and as new staff come on board with projects or project staff turnover (or need refresher training), recorded training material can be shared and accessed with follow-up one on one training with the primary local evaluator and the MER LOB Lead.

**Table 12: Tracking participants and reducing attrition**

For each wave of data collection listed in IIIA.2, what is your estimated response rate?	Entrance	100% - done at the time of enrollment
	Follow-Up	70% - estimated 1 year follow-up rate

AVANCE Houston FRAMEWorks Program Evaluation

Statistical Analysis Plan

2/6/2024

Clinicaltrials.gov ID:
NCT05261802

IV. Data Analysis

A. Data analysis

The local evaluators will run linear or logistic regression analyses to assess changes in participant outcomes after FRAMEWorks Program participation. Survey items will be explored individually and as part of constructs (e.g., parenting behaviors) that have been validated by confirmatory factor analysis. Relevant co-variables will be included in the models as controls. The evaluation team will continue to work with the program's ETAP to refine analytical methods.

To answer the ancillary question of potential differences between participants who participate virtually vs. in person, the local evaluators also plan to conduct an exploratory analysis of the moderating effect of delivery format.

Data analysis

Overview: The primary analysis for this descriptive study is to assess changes in outcomes presented in Table 2 after participation in the FRAMEWorks Program primary services. Changes in attitudes and behaviors are assessed by comparing participant responses on the OLLE and nFORM Healthy Marriage Adult Program Survey pre-surveys to participant responses on program exit surveys (OLLE and nFORM) and the OLLE 1-year follow-up survey.

Analysis begins by creating indices for constructs that will serve as the dependent variables. Constructs comprise the relevant behavioral or attitudinal survey items on the nFORM and OLLE surveys. All constructs have been confirmed with psychometric evidence derived from confirmatory factor analysis (CFA) or have already been supported by evidence of reliability and validity. Indices will be created by adding together the response codes for each of the scaled items within a given construct.

In addition to changes in the outcomes outlined above, exploratory analyses of differences in program format (weekly workshops compared to weekend retreat), virtual vs in-person, gender, and dosage are possible.

Step 1: Index scores will be compared between a participant's pre-survey and post-survey responses, and again between a participant's pre-survey and follow-up survey responses. Paired statistical tests will be used to determine if changes in outcomes between waves of data collection are significant ($p < 0.05$). The primary change of interest in this study is the difference between pre-survey responses and follow-up survey responses to see if changes persist long after program participation.

Step 2: To further explore how individual characteristics (e.g., gender), programmatic differences (e.g., virtual compared to in-person workshop delivery; weekly compared to weekend schedule format), and program dosage (e.g., number of primary hours received) may interact with program participation to create change in the outcomes of interest, a secondary analysis will be done using regression modeling. The data will be examined before analysis to determine if linear regression is appropriate. Statistical significance will be measured at the $p < 0.05$ level. The independent variables for this analysis will be a dosage measure quantifying the number of primary programming hours received and dummy variables for delivery method. Self-reported demographic characteristics will be taken from the nFORM Applicant Characteristics Survey (ACS) to be included as co-variates in the model. This will be an exploratory analysis and is not attempting to make a causal inference about the impact of program dosage or delivery method.

IRB/protection of human subjects

MER has received Institutional Review Board (IRB) approval from Solutions IRB to conduct this descriptive evaluation.

Solutions IRB, a private commercial Association for the Accreditation of Human Research Protection Programs Inc. (AAHRPP) fully accredited Institutional Review Board, will ensure that this study is approved before any research activities take place. MER has had 14 research studies approved by Solutions IRB over the past four years, has completed over 15 annual check-in reports, and has submitted timely amendments when changes to studies needed to take effect.

All submissions are completed online, so turnaround for a new study approval is between 24 to 72 hours, though the full approval process can take approximately one to two weeks depending on the number of questions and requested revisions that the IRB makes. In the IRB application submission, we will include descriptions of project staff, locations of study sites, the funding source, incentives, summary of activities, participant population, recruitment plans, risks and benefits, confidentiality of data, and the informed consent process along with all materials to be used in the study such as participant forms and surveys.

See Appendix C for Federal Wide Assurance.

Data

Table VC.1: Description of Databases

Database Name	Data Entered	Process for Data Entry
nFORM	Outcome and program performance measurement data	Entered directly by participants and FRAMEWorks Program staff
Qualtrics	Local evaluation data, participant outcomes	Entered directly by participants and by MER evaluation staff

Table VC.2: Data reporting, linking, and transfer

Database Name	Ability to Export Individual Reports?	What identifying information is available to facilitate linking to other data sources?
nFORM	Yes	nFORM Client ID, Name, DOB
Qualtrics	Yes	nFORM Client ID, Name, DOB

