## Evaluation of AVANCE-Houston FRAMEWorks Project In Houston, Texas

### I. Research Question(s)

#### A. Background

Houston, located in Harris County, Texas, is one of the fastest growing and most diverse metropolitan areas in the country, yet 15% of the population of Harris County lives in poverty. Factors such as low educational attainment, financial instability, unemployment, domestic and intimate partner violence, and homelessness contribute to the poverty and create barriers that make it difficult for adults to meet their obligations as partners, parents, and providers. Research has shown that healthy, stable families can prevent or buffer against these barriers. AVANCE-Houston aims to promote healthy family relationships and economic stability among the diverse population of Harris County, particularly those in areas with a high number of single-family households, high poverty rates, low educational attainment, and high incidence of domestic violence.

AVANCE-Houston's FRAMEWorks (Family, Relationship, and Marriage Education Works) Program seeks to accomplish these goals by providing the *Survival Skills for Healthy Families (SSHf)* curriculum to cohorts of low-income adults. Developed in 1980 by Family Wellness, this curriculum has been delivered to over 2,000,000 around the world by a variety of trained instructors and through organizations such as schools, social services, and churches. Curriculum delivery by AVANCE follows the below schedule:

- Session 1 – *All Aboard* (Program Intro)
- Session 2 – *Talk to Me* (Communication & Conflict Resolution)
- Session 3 – *Love Doesn't Hurt* (Domestic Violence)
- Session 4 – *Family Matters* (Parenting / Co-Parenting and Family Wellness)
- Session 5 – *Igniting Pathways* (Career Readiness / Advancement)
- Session 6 – *For the Love of Money* (Financial Literacy)
- Session 7 – *Me, myself, and I* (Self-Care & Family Balance)

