Target populations have included the military, refugees, foster/adoptive families, grandparents raising grandchildren, fathers, low-income adults, and has included various races/ethnicities. This evidence-based curriculum is delivered through a series of workshops that focus on communication skills, conflict resolution, knowledge of the benefits of marriage, stress and anger management, parenting skills, financial literacy, job and career advancement, and relationship skills to improve family and economic stability. Research conducted on the Family Wellness model, which includes the SSHf as its base, shows significant positive changes across racial/cultural, socioeconomic, and geographic regions associated with attending classes. One study conducted on the St. Louis Marriage Coalition consisted of 234 participants, most of whom were at-risk urban African American, Bosnian, and Hispanic mothers and fathers. Researchers concluded that the program is making progress toward one of the program objectives of “decreased number of adversarial relationships between parent partners”. The second study was conducted on the Healthy Marriage Initiative in New

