AVANCE has delivered the SSHF curriculum in part since 2009 and completely since 2015, with a target population of low-income adults residing in the Houston area. AVANCE now offers the SSHF curriculum in multiple delivery models: in recurring weekly workshops and intensive weekend retreats. As well, AVANCE will offer the weekly workshops either virtually via Zoom or in-person, while the weekend retreat will only be offered in-person due to the importance of activities designed to provide intense connection between participants. Each of these models meets the needs of the target population in different ways, and allows participants to consider factors such as childcare, transportation, work/school schedules, weekend availability, and geographic location when choosing their preferred model. All workshop models will be offered to program participants who will have the choice of whether the weekly (either in-person or virtually) or the weekend (in-person only) format works best for them. Delivering the SSHF curriculum in a virtual setting is a novel method of offering participants the information, which AVANCE hopes will add great value to the field.

The key goal of this descriptive evaluation is to assess the extent to which participation in the FRAMEWORKS Program is associated with improved attitudes and behaviors among program participants. Change will be measured from the time of program enrollment to one-year after enrollment, to allow for investigation of long-term outcomes. Research questions will focus on whether attitudes and behaviors related to parenting, partner relationships, and financial and job readiness change after participation in program services. Additionally, a secondary analysis will focus on the ancillary question of whether differences in outcomes exist between participants selecting in-person and virtual groups.

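### The curriculum is taught to cohorts, but the tests of change for R1–R6 and of delivery format make no allowance for correlation within cohorts

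*SAP*

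**What the plan says.** **Delivery is in groups.** Protocol I.A (Background) describes giving the "curriculum to cohorts of low-income adults". The formats are described as "in recurring weekly workshops and intensive weekend retreats". The retreats are held in person only, because of "activities designed to provide intense connection between participants". Participants choose their format.

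**Analysis is by individual.** Table 6 (Protocol II.C) names the individual as the unit of analysis. In SAP IV.A, Step 1 states that "Paired statistical tests will be used to determine if changes in outcomes between waves of data collection are significant", with p<0.05 as the threshold and baseline to one-year follow-up as the change of main interest. Step 2 is an exploratory regression, also judged at p<0.05. Its independent variables are "a dosage measure quantifying the number of primary programming hours received and dummy variables for delivery method", with demographic covariates.

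**Status of the questions.** Table 3 labels R1–R6 confirmatory, meaning that conclusions will rest on them, and R7 (virtual versus in-person) exploratory. Table 5 says that the analyses will decide whether changes are statistically significant.

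**What is absent.** Neither document mentions a cohort, facilitator or site effect, an ICC, a mixed model, generalised estimating equations or cluster-robust variance.

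**The concern.** A paired test removes correlation between two measurements on the same person. It does nothing about correlation between different people whose changes share a cause. Members of one cohort share sessions, group dynamics and calendar period. If that makes their changes alike, each further member of a cohort adds less information than an independent participant would, and a standard error computed over individuals is too small.

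Two sets of results are exposed. The first is the mean change for each of the six confirmatory questions, where p<0.05 is the decision rule. The second is the Step 2 format terms (virtual versus in-person, weekly versus weekend), because format is fixed by the workshop attended. At stake is a change declared significant more often than the nominal 5% when there is no true change.

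**Working it through.** **Inputs from the documents**
- Significance level 0.05 (SAP Steps 1 and 2). Sidedness is not stated; two-sided is assumed.
- One-year response 70% (Protocol Table 12).

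**Assumed, because the documents give no figure**
- 10, 15 or 20 enrolled per cohort. At 70% follow-up the number analysed per cohort is m = 7, 10.5 or 14.
- ICC of the individual change score from 0 to 0.10.

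The supplied text contains no power calculation, effect size or standard deviation, so there is no design figure to reproduce. As a check, the formulas below return exactly 5.0% at ICC 0.

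**Formulas**
- Design effect: DEFF = 1 + (m − 1) × ICC
- Factor by which the unadjusted standard error is too small: √DEFF
- True two-sided type I error: 2 × [1 − Φ(1.96 / √DEFF)]

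**Worked case** (15 enrolled, ICC 0.05): m = 15 × 0.7 = 10.5. DEFF = 1 + 9.5 × 0.05 = 1.475 and √DEFF = 1.214. Then 1.96 / 1.214 = 1.614, and the true type I error is 10.7%.

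**Range: true type I error at nominal 5%**

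| ICC | m = 7 | m = 10.5 | m = 14 |
|---|---|---|---|
| 0 | 5.0% | 5.0% | 5.0% |
| 0.01 | 5.7% | 6.1% | 6.5% |
| 0.02 | 6.4% | 7.2% | 8.1% |
| 0.05 | 8.6% | 10.7% | 12.7% |
| 0.10 | 12.1% | 16.1% | 19.6% |

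For the non-zero ICCs, the standard-error factor runs from 1.03 (ICC 0.01, m = 7) to 1.52 (ICC 0.10, m = 14).

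**Simulation check.** Set-up: 40 cohorts of 15 enrolled, each member followed up with probability 0.7, normal change scores with no true effect, half the cohorts in each format, 4,000 runs per ICC. The number of cohorts is also an assumption. Monte Carlo standard error near 5% is √(0.05 × 0.95 / 4000) = 0.34 percentage points.

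| ICC | Paired test, unadjusted | Format contrast, unadjusted | Covariate varying within cohort (such as gender), unadjusted |
|---|---|---|---|
| 0 | 4.8% | 5.2% | 4.4% |
| 0.01 | 6.3% | 6.0% | 4.9% |
| 0.02 | 7.3% | 7.8% | 5.4% |
| 0.05 | 10.8% | 10.6% | 4.5% |
| 0.10 | 15.5% | 16.7% | 5.1% |

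The paired-test column agrees with the formula at m = 10.5. The format contrast is inflated about as much as the mean change. The within-cohort covariate is not inflated.

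**With the repair.** Using cohort-clustered variance and a t reference (K − 1 degrees of freedom for the mean change, K − 2 for format, K = number of cohorts), simulated type I error over the same ICCs was 4.8–5.3% for the mean change and 5.0–5.9% for the format contrast.

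**The case against.** **The size is unknown and may be small.** The relevant ICC is that of within-person change over a year, and pairing already removes stable differences between cohorts. The documents give no ICC or cohort size and do not say whether workshop membership is fixed. At ICC 0.01 the error is only about 6%. All of this stands. A reader might infer that the tests are certainly invalid at 5%, but the documents support only a conditional statement.

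**The plan is silent rather than wrong.** The SAP names its tests in general terms and says that methods will be refined with the program's ETAP. Nothing rules out clustered errors. That is fair, but the sentence does not mention clustering, and a paired test or regression run as named would ignore it.

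**The study is descriptive, and Step 2 is exploratory.** This lowers the stakes for the format terms. It does not cover R1–R6, which are labelled confirmatory and judged by a significance rule.

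Several stronger readings are tempting and do not hold:
- *Error of 7% to 25%.* Using all 10 to 20 enrolled members with ICC 0.02–0.10 gives 7.1% to 25.0%. The primary comparison is at one year, where the protocol expects 70% to respond; the same ICCs then give 6.4% to 19.6%.
- *R7 is worse affected than R1–R6.* The simulation shows similar inflation for both.
- *Every regression term is affected.* Covariates that vary within cohorts are not. Hours received vary partly between and partly within cohorts; that term was not simulated and no figure is claimed.
- *Confidence intervals will be too narrow.* The SAP plans significance tests and mentions no intervals.
- *Couples add a second layer of clustering.* The documents do not say that partners enrol together, so this can only be a contingency.

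**Conclusion.** The concern holds in conditional form. Delivery is to cohorts, analysis is by individual, and no allowance for clustering is specified. If one-year changes are positively correlated within cohorts, the unadjusted standard errors for the R1–R6 mean changes and the delivery-format terms are likely too small, and p<0.05 is then more lenient than 5%.

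The size rests on assumed cohort sizes and ICCs. Over the range examined it runs from no inflation to a true type I error of about 20%, with 10.7% for 15 enrolled and ICC 0.05. That last case is illustrative, since nothing in the documents makes it the most likely one. The calculation also assumes similar cohort sizes and enough cohorts for the normal approximation. The repair is cheap and changes little if the ICC proves near zero, so it is worth making before the analysis.

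**What to change.** 1. Record a workshop cohort ID for every participant. Both databases already carry the nFORM Client ID (SAP Table VC.2), through which it can be attached.
2. In Step 1, test the R1–R6 changes with cohort-level cluster-robust standard errors and a small-sample correction, or with a cohort random effect on the change score. For the yes/no financial and job items, use a clustered equivalent of the paired test.
3. In Step 2, apply the same treatment to the delivery-format terms.
4. Report the number of cohorts, their sizes and the estimated ICC for each outcome.
5. Only if both partners of a couple enrol, also record a couple ID and account for it. Cohort-level clustering already covers couples who attend the same cohort.
6. If the planned sample size was derived assuming independent participants, recheck it against the design effect.

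The cost is a few sentences in the SAP, one ID field and somewhat larger standard errors: at 10.5 analysed per cohort, a factor of about 1.05 at ICC 0.01, 1.21 at 0.05 and 1.40 at 0.10. No change to recruitment, delivery or survey content is needed.
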